4.8 Handling of missing data in the analyses

IGF-1 and IGFBP-3 serum levels which are found to be below the level of detection will be imputed as one-half of the lower limit of detection for the corresponding analysis.

If for any laboratory parameter (hematology, blood chemistry, thyroid) a < or > sign is documented, this sign will be listed only. For calculation of summary tables, the respective value without sign will be used.

For safety or other efficacy parameters, missing values will not be imputed.

4.9 Analyses during an ongoing study

No interim analysis was finalized when the study was prematurely terminated.

5 References for SDS calculations

5.1 BMI SDS

As the probability distribution of the BMI is skewed, a satisfying description of the BMI needs additional characterization of the skewness. This is usually done by the LMS method (Cole and Green 1992). If the same reference for height and weight also included BMI reference values they were used. If the reference for height and weight does not include BMI reference values they were appropriately derived from height and weight.

The following references for the calculation of BMI SDS will be used in each country:

Country	Literature reference

5.2 Height SDS

Standard Deviation Scores (SDS) are the relative deviation from the mean value of normally growing children of same gender and chronological age. In general, the SDS values for height will be calculated according to the following formula $SDS = (X1 - X2) / SD$, where X1 means the measured value, X2 the mean value for the relevant chronological age and gender, and SD the standard deviation for the relevant chronological age and gender applying the references as outlined below. If respective national references are provided as median and 3rd percentiles SDS values will be calculated according to the following formula: $SDS = (X1 - X3) / (0.5 * (X3 - X4))$, where X1 means the measured value, X3 the median value for the relevant chronological age and gender, and X4 the 3rd percentile for the relevant chronological age and gender applying the references as outlines below. Resulting SDS values will be rounded to two digits. In case age is higher than maximum age in the respective reference, maximal age will be used for the calculation.

Standardization of patients' height will be performed using the following national reference:

Country	Calculation	Literature reference

To derive reference values for age groups in between the age groups reported in literature, the original tables were extended by linear interpolation between the reported values for mean and standard deviation. Final height SDS will be calculated according to national reference ranges (using the reference values for 18 year olds or older age if available).

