4.1 General considerations

Data transfer from EP00-401

Some information for analyses planned in the protocol is not provided in the CRF of this follow-up study, but in the CRF of study EP00-401 only. Therefore, the following variables provided in the CRF of EP00-401 will be transferred to this study:

- age at final visit
- gender and race
- physical examination and pubertal status at final visit
- height, height Standard Deviation Score (SDS) at final visit
- weight and BMI, BMI SDS at final visit
- fasting plasma glucose, OGTT results, fasting plasma insulin, HbA_{1C} at final visit
- IGF-I, IGFBP-3, IGF-1 SDS, and IGFBP-3 SDS at final visit
- anti-rhGH antibody testing at final visit
- safety lab at final visit
- blood pressure and pulse at final visit
- exposure to study drug

Data of study EP00-401 will be transferred to EP00-402 on the same date the EP00-402 database is locked. In general, analysis data (i.e. data created for the analysis of EP00-401) will be transferred not the original CRF data.

Study days, baseline and visits

Study days are defined as date of assessment minus date of baseline visit.

Baseline is defined as final visit of study EP00-401. If no date of final visit is available, the date of F0 baseline visit of study EP00-402 will be used instead.

Analyses by visits will be based on CRF visits, i.e. F1 Month 6, F2 1 Year, F3 5 Years, and F4 10 Years/Final. The CRF visit F4 10 Years/Final will be presented as EOS (termination visit).

Conversion factors for laboratory parameters

In order to harmonize laboratory results by using the same units, some laboratory results will be converted. Corresponding conversion factors will be listed by parameter and will provide CRF unit, SI unit and conversion factor. If albumin is given in %, the respective values will be converted to g/l using total protein values.

[figure not shown]

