4.4 Demographics and baseline characteristics

4.4.1 Demographics

Following demographic and baseline characteristics are summarized for patients in full analysis set (FAS).

Continuous variables: Age at baseline, baseline height, baseline height SDS (for further details: Section 5.2), baseline weight, BMI and BMI SDS at baseline (for further details: Section 5.1). BMI is calculated by [weight in kg] divided by [height in m]².

Categorical variables: Gender, ethnic origin

These demographic/ baseline characteristics will also be listed at a patient level including informed consent dates/days of first legal guardian, second legal guardian and child.

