4.7.2.2 Height measurements

The effect of treatment on height and height SDS will be evaluated by presenting absolute values for the observed values of height and height SDS at each visit. The effect of treatment on final height and final height SDS will be evaluated by presenting descriptive statistics for absolute values as well as absolute and relative changes from baseline of final height and final height SDS. The descriptive statistics for final height and final height SDS will only be calculated for the following patients:

- patients who completed study EP00-401
- females who discontinued study EP00-401 prematurely and are at least 16 years old when assessing final height
- males who discontinued study EP00-401 prematurely and are at least 18 years old when assessing final height.

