5.3 IGF-1 and IGFBP-3 SDS

Standardization of patients' IGF-1 and IGFBP-3 will be performed according to Elmlinger (2004). SDS values will be assessed according to the following formulas: $SDS = (X1 - X2) / ((X2 - X3) / 2)$ if $X1 < X2$ and $SDS = (X1 - X2) / ((X4 - X2) / 2)$ if $X1 \geq X2$, where X1 means the measured value, X2 the mean value for the relevant chronological age and gender, X3 the -2 SD value for the relevant chronological age and gender, and X4 the +2 SD value for the relevant chronological age and gender according to Elmlinger (2004).

Mean, -2 SD, and +2 SD values given by Elmlinger (2004) are provided for age intervals. These values were used as references for patients with an age equal to the mid of this age interval. For

patients with an age between two mids of age intervals, mean, -2 SD, and +2 SD values will be interpolated.

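### For references given as median and 3rd percentile, the height SDS formula treats the 3rd percentile as -2 SD, which makes every non-zero SDS 6.3% too large in magnitude under normality

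*SAP*

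**What the plan says.** SAP section 5.2 defines height SDS in general as the measured height minus the reference mean, divided by the reference SD for age and sex. It then adds a second rule: "If respective national references are provided as median and 3rd percentiles SDS values will be calculated according to the following formula". That formula is "SDS = (X1 - X3) / (0.5 * (X3 - X4" (closing brackets omitted), with "X3 the median value for the relevant chronological age and gender" and "X4 the 3rd percentile for the relevant chronological age and gender". Results are rounded to two digits. The text does not call the formula an approximation and gives no correction factor.

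Section 5.3 uses the same halving for IGF-I and IGFBP-3, but its lower limit is "X3 the -2 SD value for the relevant chronological age and gender", and the upper limit is likewise a +2 SD value.

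The resulting scores are used in two places. Section 4.7.2.2 presents height SDS by visit and "descriptive statistics for absolute values as well as absolute and relative changes from baseline of final height and final height SDS". Section 4.4.1 lists "baseline height SDS (for further details: Section 5.2" (closing bracket omitted) among the baseline characteristics. Section 4.1 says that height and height SDS at the EP00-401 final visit are carried over, and that in general "analysis data (i.e. data created for the analysis of EP00-401) will be transferred not the original CRF data".

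**The concern.** The two formulas in section 5.2 are meant to give the same quantity, so the divisor of the second has to equal one SD. Halving a distance gives one SD only when the distance is 2 SD. The 3rd percentile of a normal distribution is not 2 SD below the median; the -2 SD point is the 2.3rd percentile. The divisor is therefore too small, and scores are pushed away from zero: below-median heights look too low and above-median heights too high.

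For patients on such references this affects height SDS at each visit, final height SDS, and the absolute change from baseline in final height SDS. It also affects baseline height SDS if that was derived as section 5.2 describes. If some countries use mean and SD and others use median and 3rd percentile, pooled summaries mix two scales. The error is systematic, so a larger sample does not remove it.

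**Working it through.** The SAP states no figure on this point, so there is nothing to reproduce. The check is algebraic.

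**Inputs**
- Divisor 0.5 × (X3 - X4), with X3 the median and X4 the 3rd percentile (SAP 5.2).
- Target scale: (height - mean)/SD (SAP 5.2).
- Assumption: height is normally distributed within age and sex, so median and mean coincide. This fits the SAP's use of a single SD for height, whereas section 5.1 singles out BMI as skewed.

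**Inflation factor**
1. z(0.03) = -1.8808, so X3 - X4 = 1.8808 SD. For comparison, P(Z < -2) = 0.0228.
2. Divisor = 0.5 × 1.8808 SD = 0.9404 SD.
3. SAP score / true score = 1/0.9404 = 2/1.8808 = 1.0634.

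A child exactly on the 3rd percentile is scored -1.8808/0.9404 = -2.00 instead of -1.88.

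**Effect on individual scores**

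| True SDS | SAP formula | Error |
|---|---|---|
| -1.00 | -1.06 | -0.06 |
| -2.00 | -2.13 | -0.13 |
| -2.50 | -2.66 | -0.16 |
| -3.00 | -3.19 | -0.19 |

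**Effect on changes, both values from this formula.** For a true move from -3.0 to -1.5, the SAP gives -3.190 to -1.595. The absolute change of 1.50 becomes 1.595. The relative change stays at -50%, because the factor cancels. A true gain of 1.00 becomes 1.06.

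**Effect on a pooled mean.** Bias = share on percentile references × 0.0634 × true mean. Neither the share nor the true mean is in the SAP, so both are assumptions:

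| Share | Mean -1.0 | Mean -1.5 | Mean -2.5 |
|---|---|---|---|
| 0% | 0 | 0 | 0 |
| 10% | -0.006 | -0.010 | -0.016 |
| 25% | -0.016 | -0.024 | -0.040 |
| 50% | -0.032 | -0.048 | -0.079 |
| 100% | -0.063 | -0.095 | -0.158 |

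**Mixed scales between baseline and follow-up.** Take a patient whose true SDS stays at -2.50. If follow-up is corrected but the transferred baseline used the section 5.2 formula, the change is -2.50 - (-2.658) = +0.158, a spurious gain (0.13 at -2.00, 0.19 at -3.00). If instead the transferred baseline was on the true scale and follow-up uses the formula as written, the same arithmetic gives a spurious loss of 0.158.

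**The case against.** The strongest objection is that nothing shows the formula is used. It is conditional, and the public text does not show the contents of the country table. The paragraph after that table describes interpolating means and SDs but not percentiles, which would fit a branch that is little used or unused. This stands as a limit on reach: the affected share may be zero. It does not make the rule correct. The table does have a column for the calculation, which suggests that the method varies by country.

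A mean of -2.5 is not in the SAP, and baseline comes after growth hormone treatment, so milder values are plausible. This is fair. The biases at -1.0 and -1.5 are correspondingly smaller, but the 6.3% factor does not depend on the mean.

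Treating the 3rd percentile as roughly -2 SD may have been deliberate. The SAP does not say so, and an error of 0.13 at a true SDS of -2.00 is far larger than the two-digit precision it reports.

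Height SDS is secondary and descriptive. It is not used to define diabetes, the analysis sets or the patients included in the final height summaries. Raw heights are reported alongside and are unaffected. All of this stands and keeps the point below a critical one. With no inferential test planned, however, the descriptive values are themselves the result.

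Finally, changing the constant in this study alone could break comparability with EP00-401. That is a reason to align both studies, not to keep the error.

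**Conclusion.** The formula is wrong as written. Under normality of each reference, every non-zero height SDS computed with it is 6.3% too large in magnitude before rounding, and so is every absolute change in SDS when both values use it. Relative change is unaffected in that case. Across the assumed shares and means shown, the bias in a pooled mean lies between 0 and -0.16. The number of patients affected cannot be determined from the SAP. The primary diabetes endpoint is not involved. The point should be corrected because it is a stated rule that yields wrong values, although its consequences are modest.

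**What to change.** 1. Confirm from the country table which references, if any, are supplied as median and 3rd percentile.
2. For those, replace the formula with SDS = (X1 - X3) / ((X3 - X4)/1.881), which is the same as a divisor of 0.532 × (X3 - X4).
3. If a source's lower value is really its -2 SD value, keep the 0.5 and correct the definition of X4.
4. Check how the height SDS transferred from EP00-401 was derived. Where it used the same formula, recompute it from the transferred height so that baseline and follow-up share one scale. Do not correct follow-up alone.

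The cost is one constant in the SAP and the program, recalculation of baseline and follow-up SDS for the affected countries, and a short note explaining small differences from values reported in EP00-401.

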5.3 IGF-1 and IGFBP-3 SDS

Standardization of patients' IGF-1 and IGFBP-3 will be performed according to Elmlinger (2004). SDS values will be assessed according to the following formulas: $SDS = (X1 - X2) / ((X2 - X3) / 2)$ if $X1 < X2$ and $SDS = (X1 - X2) / ((X4 - X2) / 2)$ if $X1 \geq X2$, where X1 means the measured value, X2 the mean value for the relevant chronological age and gender, X3 the -2 SD value for the relevant chronological age and gender, and X4 the +2 SD value for the relevant chronological age and gender according to Elmlinger (2004).

Mean, -2 SD, and +2 SD values given by Elmlinger (2004) are provided for age intervals. These values were used as references for patients with an age equal to the mid of this age interval. For

patients with an age between two mids of age intervals, mean, -2 SD, and +2 SD values will be interpolated.

